10.1.3 Reporting Adverse Events

Table 4 Guidelines for Routine Adverse Event Reporting for Phase 2 Studies (Regardless of Expectedness)

Attribution	Grade 1	Grade 2	Grade 3	Grade 4
Unrelated			X	X
Unlikely			X	X
Possible	X	X	X	X
Probable	X	X	X	X
Definite	X	X	X	X

Routine AEs occurring between the start date of intervention until 30 days after the last intervention or until the event has resolved, the study participant is lost to follow-up, the start of a new treatment, or until the study investigator assesses the event(s) as stable or irreversible, will be reported. New information will be reported after it is received.

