- 4. The End of Treatment visit should be performed within 30 days (± 3 days) after last study drug dosing, or prior to initiation of alternate therapies (whichever occurs sooner). Follow-up and documentation of adverse events and concomitant medications should continue through day 30 (± 3 days), or until lost to death or follow-up.
- 5. Patients who discontinue study treatment should be followed on study for survival, with visits or phone contact every 12 weeks (±4 weeks) until death or lost to follow-up.

- 6. Hematology: CBC with differentials, platelets.
- 7. Chemistry: (CMP) defined as: chloride, CO₂, potassium, sodium, BUN, glucose, calcium, creatinine, total protein, albumin, total bilirubin, alkaline phosphatase, AST, ALT, A/G ratio, BUN/creatinine ratio, osmol (Calc), anion gap.
- 8. Pregnancy test is required for women of child bearing potential only. A serum pregnancy test must be performed during screening. If the serum pregnancy test is not performed within 7 days of dosing on Priming Phase V1-Day 1, a urine pregnancy test must be performed on Priming Phase V1-Day 1 with results reviewed prior to dosing. Testing may be repeated throughout the study as indicated.
- 9. Blood: six 10 mL green top tubes and one 3.5 mL gold top tube to be collected for in vitro immunological assays (see Section 8.2).
- 10. Brain MRIs must be obtained from the postoperative period (ideally with 72 hours) and post-chemoradiation period (within 1-14 days of completion of chemoradiation).
- 11. Subsequent to progression, medication review is limited to new anti-cancer regimens.
- 12. Documentation of adverse events occurring from the date the participant signs the study consent until 30 days after the last intervention or a new treatment is started, whichever occurs first. Any serious adverse event occurring any time after the reporting period must be promptly reported if a causal relationship to study treatment is suspected.
- 13. HLA –A low resolution panel
- 14. MMSE: Mini Mental State Exam will be done at the discretion of the PI. (41)
- 15. Patient to be instructed to check injection site for 24 to 48 hr post injection: staff to call within 3 to 5 days to document any reaction (see **Section 6.1.1**).

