10 SAFETY EVALUATION

10.1 Adverse Events

10.1.1 Definition

An adverse event or adverse experience (AE) is any untoward medical occurrence associated with the use of a drug in humans, whether or not considered drug related. Therefore, an AE can be ANY unfavorable and unintended sign (including an abnormal laboratory finding), symptom, or disease temporally associated with the use of a medicinal (investigational) product, whether or not considered related to the medicinal (investigational) product (attribution of 'unrelated', 'unlikely', 'possible', 'probable', or 'definite').

An AE is considered "unexpected" if it is not listed in the investigator brochure or is not listed at the specificity or severity that has been observed; or if an investigator brochure is not required or available, is not consistent with the risk information described in the general investigational plan in other study-related documents.

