12.8 Adverse Event

AEs will be coded using the latest available version of the Medical Dictionary for Regulatory Activities (MedDRA). AEs will be summarized for each treatment arm by the number and percentage of patients who experienced the event, according to system organ class and preferred term. Additional summaries will also be provided by severity grade and relationship to study drug, and for SAEs and events resulting in the permanent discontinuation of therapy. A patient reporting multiple cases of the same AE will be counted once within each system organ class and similarly counted once within each preferred term, and adverse events will be graded by worst severity grade. Unless specified otherwise, the denominator for these calculations will be based on the number of patients in each treatment arm who receive at least one dose of study drug, irrespective of the total number of doses administered. All participants who receive any study treatment will be considered evaluable for toxicity.

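### Table 4 drops Grade 1–2 events rated unrelated or unlikely from routine reporting, while 12.8 tabulates all events by grade and relationship; the plan does not say which rule governs the adverse event form

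*Combined protocol and SAP*

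**What the plan says.** Four places bear on this.

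- **Section 10.1.3, Table 4**, titled "Guidelines for Routine Adverse Event Reporting for Phase 2 Studies (Regardless of Expectedness", crosses five attributions with Grades 1 to 4. Every Grade 3 and Grade 4 cell is marked. At Grades 1 and 2 only the possible, probable and definite rows are marked. The text below it sets the window: "Routine AEs occurring between the start date of intervention until 30 days after the last intervention", or until one of several other end points.
- **Section 12.8** states: "AEs will be summarized for each treatment arm by the number and percentage of patients who experienced the event". It adds: "Additional summaries will also be provided by severity grade and relationship to study drug". The denominator is patients "who receive at least one dose of study drug, irrespective of the total number of doses administered". Neither sentence limits the tables by grade or attribution.
- **Section 10.1.1** defines an adverse event as "any untoward medical occurrence associated with the use of a drug in humans, whether or not considered drug related".
- **Table 3, footnote 12** (Section 8.1.4) calls for "Documentation of adverse events occurring from the date the participant signs the study consent until 30 days after the last intervention" or the start of a new treatment, with no grade or attribution filter.

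Serious adverse events follow their own rule. Section 10.2.2 requires all new ones in its window to be reported, and Section 15.1 has them entered on the adverse event page as well as on the serious event form.

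**The concern.** A table of patients who experienced an event is read as all-cause incidence. If low-grade events reach the database only after an investigator has rated them at least possibly related, the Grade 1–2 figures measure attribution as well as occurrence. The trial is open-label with a single arm, so nothing offsets that judgement.

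Safety and tolerability of SurVaxM alongside temozolomide is a secondary objective, and most events in the phase I trial were Grade 1 (Section 1.8.2). Low-grade tables are therefore where much of the tolerability description will sit. Cause is also hard to separate here. Section 10.1.2 puts events explained by concomitant drugs in the unrelated or unlikely classes, and Section 1.4.4 lists fatigue, nausea, headache and rash among the common reactions to temozolomide. A Grade 2 fatigue ascribed to temozolomide could fall outside Table 4 if temozolomide is treated as a concomitant drug. Section 1.4 lists it under study drugs, so even that is not settled.

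The trial is multi-center. One site could follow Table 4 and another footnote 12, and low-grade rates would then vary with site practice.

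**Working it through.** The plan states no figure that depends on this point, so there is nothing to reproduce. The check is a comparison of rules, followed by an illustration.

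**Step 1: what Table 4 omits.** 5 attributions × 4 grades = 20 cells. Marked: 2 attributions × 2 grades + 3 attributions × 4 grades = 4 + 12 = 16. Blank: 20 − 16 = 4. All four are unrelated or unlikely at Grade 1 or 2, so 4 of the 10 low-grade cells are blank.

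**Step 2: what 12.8 needs.** Incidence by preferred term, and the tables by grade and relationship, need events from all 20 cells.

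**Step 3: which rule governs the form.**

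| Place | Grade or attribution filter? | Start of window |
|---|---|---|
| 10.1.3, Table 4 (routine reporting) | Yes, at Grades 1–2 | Start of intervention |
| Table 3, footnote 12 (documentation) | No | Consent |
| 10.1.1.1, 10.1.1.2, 10.1.1.4 (recording on the form) | No | Not stated |
| 10.1.1.3 (laboratory abnormalities) | No; clinically significant and needing active management only | Not stated |
| 10.2.2 and 15.1 (serious events) | No | Consent (10.2.2) |

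No section says whether Table 4 limits entry on the form or only what is routinely reported.

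**Step 4: size if Table 4 governs entry (assumed values).** Let p be the true share of treated patients with a given Grade 1–2 term. Let u be the share of those patients whose events of that term were all non-serious and all rated unrelated or unlikely. Section 12.8 counts a patient once per preferred term, so a patient with one related and one unrelated episode stays in the numerator. This is why u is a share of patients, not of events.

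Tabulated incidence = p × (1 − u)

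With p = 40%:

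| u | Tabulated incidence | If 50 treated (true 20) | If 65 treated (true 26) |
|---|---|---|---|
| 0.25 | 0.40 × 0.75 = 30% | 15 | 19.5 |
| 0.50 | 0.40 × 0.50 = 20% | 10 | 13 |
| 0.75 | 0.40 × 0.25 = 10% | 5 | 6.5 |

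The 50 is the evaluable target and the 65 the enrolment ceiling in Section 12.1; the number treated is not stated. The percentages do not depend on it. The proportional loss is u whatever the value of p.

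**Step 5: size if footnote 12 governs entry.** All events are on the form, the tabulated incidence is p, and nothing is lost.

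**Step 6: what is untouched either way.** Every Grade 3–4 cell is marked, so the Grade 3 or 4 toxicity endpoint (Section 12.3) and its rate with confidence interval (Section 12.7.1, secondary analyses) are complete. Serious event summaries are complete under Sections 10.2.2 and 15.1.

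**The case against.** The strongest reply is that Table 4 is a reporting guideline, not a rule on data entry. The sections on documentation and recording carry no attribution filter. Section 10.1.1.3 restricts form entry explicitly for laboratory values, so the authors wrote a recording filter where they wanted one. Section 10.1.2 has the investigator rate relationship on all five levels with no grade limit. This stands: the documents do not establish that low-grade incidence will be understated. They leave it open, because Table 4 is also the only grade-by-attribution rule for routine events and nothing says that it stops short of the form.

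A second reply is that the listed safety endpoint is Grade 3–4 and that injection-site reactions, the main expected low-grade toxicity, must be reported under Section 6.3.1.1 and would normally be rated possible or higher. This also stands, and it limits the consequence.

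A reader might infer two stronger things.

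- *Every low-grade event would appear drug-related.* It would not. A Grade 1–2 serious event rated unrelated still reaches the adverse event page, and the rating possible expressly allows for other causes.
- *The regimen would be flattered against other trials.* The plan's historical comparison is for six-month PFS only; it plans no comparison of adverse event rates.

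**Conclusion.** There is a real mismatch between a stated reporting rule and a stated analysis, and it is minor. If Table 4 governs form entry, the all-cause incidence of non-serious Grade 1–2 events in 12.8 is too low, its size turns on open-label attribution, and the Grade 1–2 unrelated and unlikely rows hold serious events only. If footnote 12 governs, there is no bias, and the defect is that the protocol does not say so.

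The 30% to 10% range against a true 40% rests on an assumed incidence and an assumed 25% to 75% share of patients; neither comes from the documents. It shows that the effect could be visible in a table, not that it will occur.

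**What to change.** Reconcile Table 3, footnote 12 with Section 10.1.3, including whether the window opens at consent or at the start of intervention. Then choose one of two routes.

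(a) State beside Table 4 that adverse events of every grade and attribution are entered on the adverse event form, and that Table 4 concerns routine reporting only. Section 12.8 then stands as written. Cost: some extra data entry at sites.

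(b) Keep Table 4 as the rule for entry and amend 12.8. All-cause summaries and the unrelated and unlikely rows would cover Grade 3 and above plus serious events of any grade. Non-serious Grade 1–2 events would go in a table titled *at least possibly related*, keeping the split into possible, probable and definite that Table 4 does collect. Cost: wording and table titles only, but no all-cause low-grade incidence can then be claimed.

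Route (a) keeps the analysis that 12.8 describes; route (b) makes the tables say what they contain.

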10.2 Serious Adverse Events

10.2.1 Definition

A serious adverse event (SAE) is any adverse event (experience) that in the opinion of either the investigator or sponsor results in **ANY** of the following:

- Death.
- A life-threatening adverse event (experience). Any AE that places a participant or participant, in the view of the Investigator or sponsor, at immediate risk of death from the reaction as it occurred. It does **NOT** include an AE that, had it occurred in a more severe form, might have caused death.
- Inpatient hospitalization or prolongation of existing hospitalization (for > 24 hours).
- A persistent or significant incapacity or substantial disruption of the ability to conduct normal life functions.
- A congenital anomaly or birth defect.
- Important Medical Event (IME) that, based upon medical judgment, may jeopardize the participant and may require medical or surgical intervention to prevent one of the outcomes listed above.

10.2.2 Reporting Serious Adverse Events

All new SAEs occurring from the date the participant signs the study consent until 30 days after the last intervention or a new treatment is started, whichever comes first, will be reported. The RPCI SAE Source Form is to be completed with all available information, including a brief narrative describing the SAE and any other relevant information.

SAEs occurring after the 30 day follow-up period that the investigator determines to be possibly, probably or definitely related to the study intervention should be reported.

SAEs identified as an Unanticipated Problem by the Investigator must be reported. Please refer to Section 10.4 for details on reporting Unanticipated Problems.

10.3 Follow-Up for Serious Adverse Events

All related SAEs should be followed to their resolution, until the study participant is lost to follow-up, the start of a new treatment, or until the study investigator assesses the event(s) as stable or irreversible. New information will be reported when it is received.

10.4 Unanticipated Problems

10.4.1 Definition

An Unanticipated Problem (UP) is any incident, experience, or outcome that meets all of the following criteria:

• Unexpected (in terms of nature, severity, or frequency) given:

- a) The research procedures that are described in the study-related documents, including study deviations, as well as issues related to compromise of participant privacy or confidentiality of data.
- b) The characteristics of the participant population being studied.
- Related or possibly related to participation in the research (possibly related means there is a reasonable possibility that the incident, experience, or outcome may have been caused by the procedures involved in the research).
- Suggests that the research places participants or others at a greater risk of harm (including physical, psychological, economic, or social harm) than was previously known or recognized and if in relation to an AE is also deemed **Serious** per **Section 10.2**.

10.4.2 Reporting Unanticipated Problems

Unanticipated problem reporting will begin at the time of participant consent. The Unanticipated Problem Form will be submitted to the CRS Compliance Office within 1 business day of becoming aware of the Unanticipated Problem.

When becoming aware of new information about an Unanticipated Problem, submit the updated information to CRS Compliance with an updated Unanticipated Problem Form. The site Investigator or designated research personnel will report all unanticipated problems, whether related or unrelated to the investigational agent(s) to the IRB in accordance with their local institutional guidelines.

10.5 FDA Reporting

When RPCI is the IND holder the following describes the FDA reporting requirements by timeline for AEs and new safety findings that meet the criteria outlined below:

Within 7 Calendar Days

Any adverse event that meets **ALL** the following criteria:

- Related or possibly related to the use of the study drug;
- Unexpected; and
- Fatal or life-threatening.

Within 15 Calendar Days

Any adverse event that meets **ALL** the following criteria:

- Related or possibly related to the use of the study drug;
- Unexpected; and
- Serious but not fatal or life-threatening;

Or, meets **ANY** of the following criteria:

• A previous adverse event that is not initially deemed reportable but is later found to fit the criteria for reporting (report within 15 days from when event was deemed reportable).

- Any findings from other studies, including epidemiological studies, pooled analysis of
 multiple studies, or other clinical studies conducted with the study drug that suggest a
 significant risk in humans exposed to the drug.
- Any findings from animal or in vitro testing that suggest a significant risk for human participants including reports of mutagenicity, teratogenicity, or carcinogenicity or reports of significant organ toxicity at or near the expected human exposure.
- Any clinically important increase in the rate of occurrence of a serious, related or possibly related adverse event over that listed in the protocol or investigator brochure.

Sponsors are also required to identify in IND safety reports, all previous reports concerning similar adverse events and to analyze the significance of the current event in the light of the previous reports.

Reporting Process

The principal investigator or designee will complete and submit a FDA Form 3500A MedWatch for any event that meets the above criteria. Forms will be submitted to the CRS Compliance Office via email to [contact]. Network sites: refer to Appendix A.

11 DATA AND SAFETY MONITORING

The RPCI Data and Safety Monitoring Board will assess the progress of the study, the safety data, and critical efficacy endpoints. The DSMB will review the study annually and will make recommendations that include but not limited to; (a) continuation of the study, (b) modifications to the design (c) or termination of the study.

12 STATISTICAL METHODOLOGY

12.1 Study Design

This is a multi-center, open-label; prospective one-arm phase II clinical trial evaluating the safety and efficacy of SurVaxM and adjuvant temozolomide in adult patients with newly diagnosed GBM. The statistical design is based on an assessment of the efficacy of the study treatment for patients as compared to an external standard, i.e., historical control. All enrolled patients will receive the study treatment and initiation of the treatment should take place as soon as possible following study enrollment. A total of up to 65 patients will be enrolled to meet our target of at least 50 evaluable patients. An evaluable subject is defined as a subject who meets eligibility requirements and who completes the initial four priming doses of the vaccine. If a patient signs an Informed Consent and does not receive all four priming injections or, the patient withdraws their consent before receiving the priming injections, the patient will be classified as unevaluable and will be replaced. Analyses will be performed with a focus on estimation of specific clinically important parameters for use in the planning of larger subsequent comparative trials designed to fully assess efficacy and safety.

All analyses will be performed using the SAS® statistical software system.

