3 OBJECTIVES

3.1 Primary Objective

To evaluate 6-month progression-free survival (PFS6) in patients with survivin positive newly diagnosed glioblastoma multiforme (GBM) treated with at least 4 doses of SurVaxM and standard of care temozolomide. PFS6 is defined as the percentage of patients without tumor progression or death from any cause 6 months after the date of diagnosis by biopsy.

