6.6 Treatment Discontinuation

Upon treatment discontinuation, all end of treatment evaluations and tests will be conducted. All participants who discontinue due to an AE must be followed until the event resolves or stabilizes. Appropriate medical care should be provided until signs and symptoms have abated, stabilized, or until abnormal laboratory findings have returned to acceptable or pre-study limits. The final status of the AE will be reported in the participant's medical records and the appropriate eCRF.

A patient should be withdrawn from study treatment if, in the opinion of the Investigator, it is medically necessary. In addition, patients will be withdrawn from treatment in the case of:

- 1. RANO criteria defined disease progression. In cases where RANO criteria cannot be applied, progression should be based on unequivocal evidence of progressive disease sufficient to require a change in therapy.
- 2. A need for surgery, radiation, or for other anticancer therapy not specified in the protocol.

- 3. Lost to follow-up or noncompliant.
- 4. Pregnancy. Pregnant patients should be followed for the duration of the pregnancy and the outcome of the pregnancy should be documented.
- 5 Death
- 6. Participant voluntary withdrawal
 - a. A participant may withdraw from the study at any time, for any reason. If a participant discontinues treatment, an attempt should be made to obtain information regarding the reason for withdrawal.
- 7. Investigator decision.

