9 EFFICACY EVALUATIONS

9.1 Objective Tumor Response

All protocol-defined imaging studies must be performed at the investigative site or sponsor-approved facility using protocol-defined parameters. The same method of assessment and the same technique should be used to characterize each identified and reported lesion at baseline and during follow-up. The Modified Response Assessment in Neuro-Oncology (RANO) Response Criteria (**Appendix C**) will be used to define tumor response and progression (40).

It is important to use the same method of assessment from one scan to the subsequent scans.

Rarely, patients undergoing vaccine therapy for tumor can develop an inflammatory response in the tumor bed that mimics either true tumor recurrence or pseudoprogression. If a patient who has completed the 4-dose vaccine priming phase of treatment undergoes either biopsy or re-resection of new contrast-enhancing tissue and no tumor is determined by the local neuropathologist to be present on histologic exam, the patient may continue on treatment under

protocol with approval of the lead principal investigator. If any amount of tumor is found to be present at re-biopsy, the patient must be declared to have progressed as of the date of the MRI scan that first showed the new enhancement. Patients with new enhancement during the priming phase that is not suspected to be pseudoprogression are not eligible to continue treatment on protocol.

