12.2 Study Objectives

The primary objective of this study is:

• To evaluate 6 month progression-free survival (PFS) rates in patients with survivin positive newly diagnosed GBM treated with SurVaxM and adjuvant temozolomide.

The secondary objectives of this study are:

- To determine the safety and tolerability of SurVaxM in patients receiving standard of care temozolomide.
- To evaluate overall survival (OS) in patients with survivin positive newly diagnosed GBM treated with SurVaxM and adjuvant temozolomide.
- To describe the immune response in patients treated with SurVaxM and predictors of response.
- To evaluate objective tumor response rate (applicable only for patients with evaluable disease at study entry, as defined per RANO criteria) and predictors of response.

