12.3 Study Endpoints

Primary Endpoint:

• PFS is defined as the time from date of diagnosis to the date of first observed disease progression or death due to any cause. All patients will be followed for a minimum of 6 months relative to evaluating the primary endpoint.

Secondary Endpoints:

- OS is defined as the time from date of diagnosis until date of death or the last date patient known alive (if death is not observed).
- Number of Grade 3 or 4 toxicities, according to National Cancer Institute Common Toxicity Criteria for Adverse Events (NCI CTCAEs) Version 4
- Immune responses to SurVaxM and predictors of response

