12.7 Efficacy Analysis

12.7.1 Primary Analysis

The primary objective is to evaluate the 6 month PFS survival fraction in patients with newly diagnosed GBM treated with at least 4 priming doses of SurVaxM and standard-of-care adjuvant

temozolomide as compared to historical control. PFS is defined as the time from date of diagnosis to the date of first observed disease progression or death due to any cause. Patients who are alive and disease free at the last study assessment will be treated as censored.

Historical Control: Patients in this population defined by the eligibility criteria receive standard-of-care which consists of concurrent temozolomide and radiation followed by adjuvant temozolomide. Based on provided historical information, the 6 month PFS survival fraction is assumed to be 0.55. We hypothesize that treatment with SurVaxM and adjuvant temozolomide will increase the 6 month PFS survival fraction to 0.70. Therefore the PFS survival fraction will be measured after all patients have been followed for 6 months.

The 6 month PFS survival fraction is estimated as standard binomial proportion. An exact one-sided binomial test will be used to test our primary hypothisis. The nominal significance level to be used for this test is 0.10. In addition, a Kaplan-Meier curve for PFS will be used calculated to generate summary descriptive statistics, e.g. median PFS.

Secondary Analyses

The estimated distributions of overall survival (OS), defined as the time from date of diagnosis to death due to any cause, will be obtained using the Kaplan-Meier method. Estimates of quantities such as median survival will be obtained. Corresponding confidence intervals will be computed. It is assumed *a priori* that any drop out times will be non-informative in terms of the censoring mechanism. Groups defined by levels of categorical or dichotomized numeric demographic/baseline variables will be compared in regards to time-to-event distributions using the log-rank test. Cox proportional hazards model regression will be utilized for multivariate analyses.

A summary of anticancer therapies received following the discontinuation of protocol therapy will be provided. Such therapies will be classified as chemotherapy, biological therapy, radiation, surgery, or other.

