12.9 Replacement

Patients who meet either of the following conditions will be considered unevaluable for the primary end-point and will be replaced:

- Failure to receive all 4 priming doses of SurVaxM (making a patient unevaluable for the purposes of the primary end-point), or,
- Withdrawal of consent by patient.

Up to an additional 15 patients may be enrolled to replace unevaluable patients or patients who withdraw consent prior to receiving study treatment.

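### Patients who progress or die before the fourth priming dose are dropped and replaced, so some PFS6 failures never reach the primary test

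*Combined protocol and SAP*

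**What the plan says.** **Who is analysed.** Section 12.1: "An evaluable subject is defined as a subject who meets eligibility requirements and who completes the initial four priming doses of the vaccine". Anyone without all four priming injections is replaced, within a cap of 65 enrolled for at least 50 evaluable. Section 12.9 lists as a ground for replacement: "Failure to receive all 4 priming doses of SurVaxM (making a patient unevaluable for the purposes of the primary end-point". It allows up to 15 extra patients. Neither section asks why the doses were missed.

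**What counts as failure.** Section 3.1 defines PFS6 as "the percentage of patients without tumor progression or death from any cause 6 months after the date of diagnosis by biopsy". Section 12.3 ends PFS at "the date of first observed disease progression or death due to any cause".

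**What stops dosing.** Section 6.6 lists "RANO criteria defined disease progression" and death among the reasons for withdrawal from treatment. Section 9.1 adds: "Patients with new enhancement during the priming phase that is not suspected to be pseudoprogression are not eligible to continue treatment on protocol".

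**The benchmark.** Section 12.7.1 introduces the historical control with "Patients in this population defined by the eligibility criteria receive standard-of-care" and assumes a 6-month rate of 0.55. It mentions no dose requirement for the control.

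**The objective.** Section 3.1, the synopsis and 12.7.1 restrict the objective to patients given the four doses. Section 12.2 states it without that restriction: "To evaluate 6 month progression-free survival (PFS) rates in patients with survivin positive newly diagnosed GBM treated with SurVaxM and adjuvant temozolomide".

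**The concern.** Completing four doses is known only after treatment has started, and it depends partly on not having failed. A patient who progresses or dies before dose 4 has met the primary endpoint, yet is removed and another patient enrolled. The treated group must therefore stay on treatment through priming to be counted, whereas nothing shows that the group behind the 0.55 was selected in that way.

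This bears on the trial's only primary test. A positive result could partly reflect who was removed, and the inflated PFS6 would be carried into the comparative trials that 12.1 says these estimates are meant to help plan. No PFS6 analysis of all treated patients is specified that would reveal the effect.

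**Working it through.** **1. Are events before dose 4 always inside the 6-month window?** Sections 4.1 and 6.1 give about 4 weeks of recovery, 6 weeks of chemoradiation, 7 to 28 days to dose 1, and dose 4 on Day 43 (6 weeks after dose 1).

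- Earliest: 4 + 6 + 1 + 6 = 17 weeks after surgery.
- Latest: 4 + 6 + 4 + 6 = 20 weeks.

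Taking diagnosis as close to surgery, both fall before 6 months (about 26 weeks). On these timings, progression or death before dose 4 is a PFS6 failure.

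**2. The plan's own design.** Inputs from 12.4 and 12.7.1: exact one-sided binomial test, null 0.55, alternative 0.70, level 0.10, n = 50.

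- P(X ≥ 32 | 50, 0.55) = 0.1273, above 0.10.
- P(X ≥ 33 | 50, 0.55) = 0.0765, so the cutoff is 33/50.
- Power: P(X ≥ 33 | 50, 0.70) = 0.782.
- The smallest n with power of at least 0.80 is 49 (cutoff 32, size 0.0948, power 0.810), so the stated n = 50 is reproduced to within one patient.

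**3. Effect of the exclusion.** Let f be the share of treated patients who fail before dose 4 and are replaced. If the true PFS6 in all treated patients is 0.55 (inactive vaccine), the rate among those left in the test is 0.55/(1 − f). The false-positive rate is P(X ≥ 33 | 50, 0.55/(1 − f)). The documents do not give f, so a range is assumed.

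| f | Rate among evaluable | False-positive rate |
|---|---|---|
| 0 | 0.550 | 0.077 |
| 2% | 0.561 | 0.102 |
| 5% | 0.579 | 0.154 |
| 10% | 0.611 | 0.289 |
| 15/65 = 23% (every replacement slot used for an early failure) | 0.715 | 0.846 |

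The 0.10 level is crossed at f = 0.0186. One such patient for every 50 evaluable (1/51 = 0.0196) is enough, giving 0.1015.

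**4. Mixed reasons for exclusion.** If the remaining exclusions are unrelated to outcome, f is the excluded share times the early-failure share.

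- 10% excluded, half early failures: f = 0.10 × 0.5 = 0.05, giving 0.154.
- 15/65 excluded, a quarter early failures: f = 0.058, giving 0.171.
- 15/65 excluded, half early failures: f = 0.115, giving 0.344.

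**5. Effect on an observed result.** The smallest passing result is 33/50, p = 0.077. Restoring one replaced failure gives 33/51, p = 0.1045, which does not reject. Restoring three gives 33/53, p = 0.178. A result of 35/50 (p = 0.022) still rejects with four restored (35/54, p = 0.094) but not with five (35/55, p = 0.124).

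**The case against.** **The four-dose group is the stated target.** The synopsis, 3.1 and 12.7.1 all carry the condition, and 12.2 is the outlier. That is so, but repeating the condition does not remove the selection, and the benchmark still lacks it.

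**Few failures will be lost.** Scans are every 8 weeks (±4), so many progressors will first be detected after dose 4. Suspected pseudoprogressors may stay on treatment and be back-dated later (9.2). Both groups still count as failures. Exclusions unrelated to outcome add no bias, and excluding patients who would have been progression-free biases the other way. All of this stands and limits the claim to some failures, but about one in 51 is enough to breach the level.

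**The error rates depend on 0.55 holding in all treated patients.** True. At 0.53 with f = 5% the rate is 0.094, and at 0.50 with f = 10% it is 0.088. A true rate above 0.55 makes it worse. But 0.55 is the plan's own null, and the level of a test is judged at its null.

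**Any exact test is fragile at its cutoff.** Also true, and 35/50 withstands four restored failures. The difference is that this rule moves results in the favourable direction whenever an early failure is replaced.

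**The 23% figure is extreme.** It is an upper bound. Section 12.9 also gives those 15 slots to patients who withdraw before any treatment.

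**This is an estimation-focused phase II.** Reporting an all-treated analysis beside the four-dose set would expose the bias, but the formal test would remain biased.

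**Conclusion.** The concern holds and must be fixed. Followed as written, 12.1 and 12.9 remove from the primary test patients who have already met the primary endpoint, and compare the remainder with a benchmark that carries no such condition. The direction is upward to the extent that excluded patients are early failures. The size is unknown because the documents give no rate of progression or death before dose 4. If PFS6 in all treated patients equals the null of 0.55, the false-positive rate exceeds 0.10 from f of about 1.9%. It is 0.154 at 5% and 0.289 at 10%, with an upper bound of 0.846 at the replacement cap. The existence of the problem does not depend on these assumed shares; only its size does.

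**What to change.** - **Primary set:** all eligible patients who receive at least one dose of SurVaxM. This agrees with the objective as worded in 12.2 and with the any-dose denominator that 12.8 uses for toxicity.
- **Failures:** count progression or death before dose 4 as PFS6 failure.
- **Replacement:** replace only patients who never receive a dose. Keep four-dose completers as a labelled secondary set.
- **Cutoff:** state the number to be dosed in advance and apply the exact cutoff for the number analysed. Accrual can stop at 50 dosed patients; the larger rows apply if more are dosed.

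| n | Cutoff | Size | Power at 0.70 |
|---|---|---|---|
| 50 | 33 | 0.077 | 0.782 |
| 55 | 36 | 0.076 | 0.813 |
| 60 | 39 | 0.076 | 0.838 |
| 65 | 42 | 0.075 | 0.860 |

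Power assumes that 0.70 holds in the at-least-one-dose set.

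- **Unknown status:** say beforehand how the binomial test treats dosed patients who stop for other reasons and have no known 6-month status. Report sensitivity analyses with them scored as failures and by Kaplan-Meier.
- **Wording:** align the objective in the synopsis, 3.1, 12.2 and 12.7.1. Reconcile the timing of consent withdrawal: 12.1 says before the priming injections, the 12.9 bullet gives no time, and the last sentence of 12.9 says before study treatment.

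**Cost.** Text changes in the synopsis, 3.1, 12.1, 12.2, 12.7.1 and 12.9, within the existing cap of 65. Progression status at 6 months is needed for patients who stop before dose 4 without having progressed or died. Section 12.3 promises 6 months of follow-up for everyone, but 8.1.4 specifies only survival contact after treatment stops, so the two need reconciling. The PFS6 estimate will be less favourable wherever early failures are restored.
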